Official Title: Assessing the Safety of Nighttime Passy-Muir Valve Use and its Impact on Sleep Quality in the Long-Term Acute Care Hospital Setting: a Cross-Over Controlled Study

Clinical Trial Number: NCT06229639

Use date of study closeout: 9/1/2016

STUDY PROTOCOL AND STATISTICAL ANALYSIS PLAN

Study Protocol

Eligible participants were inpatients 18 years of age or older, who were admitted to Gaylord Specialty Healthcare following tracheostomy placement during an acute care hospital stay, were eligible for decannulation, and who had a tracheostomy tube size of six or smaller and did not require ventilation assistance. These patients were initially referred to the study by a Respiratory Care Practitioner (RCP). Patients also needed to meet all criteria outlined in Gaylord's decannulation protocol, along with the specific criteria required for the study. (**Table 1**). Eligible patients were then approached for study enrollment. Enrolled participants were given the FDA-approved PMV #2001 for the study. The PMV is a bias-closed, no-leak speaking valve that allows patients to speak at a level consistent with their normal vocalization range.

Participants were monitored and evaluated using the same outcomes and safety metrics typically used during the study site's decannulation protocol. This included an initial and daily evaluation by a Pulmonary or Critical Care Medicine consultant and daily morning arterial blood gas (ABG) measurements by an RCP. The RCP then conveyed ABG measurement to the covering therapists and Pulmonary or Critical Care Medicine consultants at shift change. The RCP then communicated daily with the covering Independent Medical Practitioner (IP). If participants failed to meet the decannulation or study criteria at any point during the protocol, then the IP was notified, and the protocol was to be canceled.

PMV Trial – Study Day One and Night One

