If study day one and night one were successful, the protocol was continued to day two. During day two, participants wore a tracheostomy cap, also known as a plug. If the plug was tolerated without any adverse response, participants were instructed to keep the tracheostomy plug in place throughout the night. Again, nursing staff monitored and recorded heart rate, blood pressure, and temperature every four hours, and the RT on duty recorded oxygen saturation, ET_{CO}₂ levels, and respiratory rate. Same as night one, if any adverse events or acute changes occurred, it was planned that the plug be removed, ventilator support would be started, and the trial considered a failure. If no adverse events occurred upon waking up following night two, the participants were again administered the RCSQ. Once completed, following night two, participants' roles in the study were done and continued with the decannulation protocol as appropriate.

Statistical Analysis

Continuous clinical and demographic characteristics were described with means and 95% confidence intervals, and categorical data were described with frequencies. Differences in categorical variables were evaluated using Fischer's exact test or Chi-Square testing as appropriate. Differences in continuous variables were analyzed using paired t-tests for normally distributed data and Wilcoxon signed-rank test for non-normally distributed data. Two-way ANOVA analysis and Tukey's multiple comparisons post-hoc test were used to analyze differences in continuous variables at three time points (22:00, 02:00, and 06:00). Complete case analysis was performed on the dataset, with only complete pairs of data from night one and night two at the three time points being included in the analysis. All data were analyzed via GraphPad Prism 9 (GraphPad Software, San Diego, CA). Statistical significance was defined as a p-value less than 0.05.

Criteria for Initiation of Decannulation Protocol and Other Study-Specific Criteria

Decannulation Criteria

Afebrile
Hemodynamically stable
Clear or stable chest x-ray
Controlled Secretions
Peak Cough Flow ≥ 160 L / m
Satisfactory on-going nutrition (low risk of aspiration)
No clinical evidence of tracheal obstruction
Ability to tolerate a speaking valve

Inclusion Criteria

Patient has evidence of respiratory insufficiency requiring a tracheostomy tube without current need for assisted ventilation.
Patient will be continuously monitored with telemetry.

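### The complete-pairs rule drops the finished valve night of anyone who stops on day two, so the valve-night results describe only participants who went on to tolerate the plug by day

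*Combined protocol and SAP*

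**What the plan says.** The order is fixed: valve first, plug second. Under the heading for day two and night two, the plan says "If study day one and night one were successful, the protocol was continued to day two". The plug is worn by day, and the night follows on a condition: "If the plug was tolerated without any adverse response, participants were instructed to keep the tracheostomy plug in place throughout the night".

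The valve-night measurements are already in hand by then. Under the heading for day one and night one, nursing staff and the respiratory therapist record the overnight readings, and the participant completes the RCSQ on waking.

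The Statistical Analysis section describes a complete case analysis, "with only complete pairs of data from night one and night two at the three time points being included in the analysis". Continuous differences are tested with "paired t-tests for normally distributed data and Wilcoxon signed-rank test for non-normally distributed data", which need a value from each night. No separate analysis set is defined for night one.

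On stopping, the plug section says "Same as night one, if any adverse events or acute changes occurred, it was planned that the plug be removed", with "ventilator support would be started, and the trial considered a failure". The Study Protocol section adds a general cancellation rule: "If participants failed to meet the decannulation or study criteria at any point during the protocol, then the IP was notified".

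**The concern.** Whether a valid valve night is analysed depends on a later daytime response to a different device. The title puts the safety of nighttime valve use first, and the protocol names sleep quality as the secondary outcome. Describing how participants did overnight on the valve does not require a plug night.

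The plan's own thresholds make selection plausible. The valve night ends in failure for serious reactions, while supplemental oxygen is noted but does not end the trial. Entry to night two is stricter, because it requires that the daytime plug cause no adverse response of any kind. A borderline valve night can therefore count as a success, and the same participant can then be lost on day two. If participants with less airway reserve tend both to have worse valve-night readings and to fail the plug by day, the less favourable valve nights are the ones removed.

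**Working it through.** The documents give no sample size, SD, effect size or loss rate, so there is no plan figure to reproduce. The check is a trace of the data, followed by illustrations on assumed inputs.

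**Trace for a participant who passes night one and stops on day two**

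| Item | Night one (valve) | Night two (plug) | Complete pair? |
|---|---|---|---|
| Readings at 22:00, 02:00, 06:00 | recorded | none | no: excluded by the stated rule |
| RCSQ | completed on waking | not given | no: lost from the paired tests |

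The exclusion is explicit for the readings at the three time points. For the RCSQ it follows from the use of paired tests.

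**Shift in the valve-night mean (all inputs assumed)**

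Let a fraction f of the N participants with a successful valve night stop on day two. Suppose they are the worst tail of a latent trait that has correlation r with a valve-night reading such as ETCO2. With z = Φ⁻¹(1 − f), the mean among those kept shifts favourably by r·φ(z)/(1 − f), in SD units. The standard error is taken as 1/√(N(1 − f)).

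For r = 0.5:

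| f | φ(z)/(1 − f) | Shift (SD) | Shift/SE, N = 20 | Shift/SE, N = 40 |
|---|---|---|---|---|
| 10% | 0.1755/0.90 = 0.195 | 0.10 | 0.4 | 0.6 |
| 15% | 0.2332/0.85 = 0.274 | 0.14 | 0.6 | 0.8 |
| 20% | 0.2800/0.80 = 0.350 | 0.18 | 0.7 | 1.0 |

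At f = 15%, the shift runs from 0.3 × 0.274 = 0.08 SD (r = 0.3) to 0.7 × 0.274 = 0.19 SD (r = 0.7).

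**RCSQ scale.** The gap between the complete-pairs mean and the mean of all who passed the valve night is f × (mean of plug-tolerant − mean of plug-intolerant). For an assumed difference of 5 to 20 mm, this is 0.5 to 2.0 mm at f = 10% and 1.0 to 4.0 mm at f = 20%.

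**Event rates.** Suppose a valve-night event such as supplemental oxygen occurred in 10% of plug-tolerant and 30–50% of plug-intolerant participants. At f = 20%, the rate among all who passed the valve night is 0.8 × 10% + 0.2 × 30% = 14%, up to 0.8 × 10% + 0.2 × 50% = 18%. The complete-pairs set would show 10%.

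**Chance that the rule removes anyone.** With 20 participants passing the valve night, the chance of at least one removal is 1 − (1 − f)²⁰: 64% at f = 5%, 88% at 10% and 99% at 20%.

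Every shift is zero if f = 0, or if those who stop do not differ from those who continue.

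**The case against.** **The size is wholly assumed.** This stands. The documents do not say that anyone stopped on day two, and the illustrated shifts are at most about one standard error.

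**The valve nights at issue were successes.** This also stands. No valve trial ended for a serious reaction is hidden by this route; what can be hidden is a less favourable set of readings below that threshold.

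**A within-patient contrast needs both nights.** True, and the complete-pairs rule is reasonable for that contrast. It is not needed for describing the valve night alone.

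**This is one branch of a general complete-case problem.** Also true. Night-two failures and missing readings remove participants in the same way, and one repair covers them all.

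A reader might go further in three directions that the documents do not support.

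- *That a daytime plug failure has no classification.* The failure sentence sits under a heading that covers both day two and night two, and it refers back to a night-one rule that applies whenever a serious reaction occurs. With the general cancellation rule, a daytime adverse response can be read as a failure. What stays unclear is whether that sentence was meant to cover the daytime, how intolerance without an adverse event is classed, and how a failure enters the analysis. The cited Figure 1 and Table 2 are not visible here and may show part of this.
- *That these participants are not counted as valve successes.* Reaching day two already requires a successful day one and night one.
- *That they vanish from every count.* The complete-pairs wording is tied to data at the three time points, and categorical data are described separately by frequencies. Nothing says that simple counts of success and failure are limited to complete pairs.

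**Conclusion.** The point holds as a matter of the analysis set. Under the stated rule, a finished valve night is excluded because of what happens later with the plug, and the valve-night results then describe only participants who reached night two and had complete data on both nights. The likely direction is towards a safer-looking valve night, provided that poor plug tolerance goes with worse valve-night readings. The documents neither show nor rule out that link.

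The size cannot be established. With a correlation of 0.5 and a 10–20% loss, both assumed, the shift is about 0.10–0.18 SD; with no loss it is zero.

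A reader might also infer that these participants amount to paired evidence that the valve is better tolerated than the plug. They do not. The plug is tried only after valve success, so a participant who fails the valve and passes the plug cannot occur. Every discordant pair must favour the valve by design, and an exact paired test on such pairs has no valid null.

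**What to change.** In the Statistical Analysis section:

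1. Summarise the valve-night readings and the night-one RCSQ for every participant who wore the valve on night one, whatever happened on day two.
2. Keep complete pairs only for the within-patient contrast of night one with night two.
3. Report descriptively the number who stopped on day two, and show their valve-night readings beside those of participants who reached night two. If nobody stopped, one line in the participant flow settles the matter.
4. Do not enter day-two plug failures in a paired valve-versus-plug tolerance test.

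The data are already recorded and no clinical procedure changes. The cost is revised wording and one extra table. The valve-night summary and the paired contrast will have different denominators, which should be labelled.

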On day one of the study period, participants were given a PMV to use during the day. If the PMV was tolerated without any acute vital changes (i.e., adverse reactions; **Table 2**), participants were instructed to keep the PMV on after 22:00, when it would typically be removed if still in place (**Figure 1**). Throughout the night, participants were kept on continuous telemetry for the duration of the study protocol. Nursing staff monitored and recorded heart rate, blood pressure, and temperature every four hours (e.g., 22:00, 02:00, and 06:00). The Respiratory Therapist (RT) on duty recorded oxygen saturation, end-tidal carbon dioxide (ETCO₂) levels via nasal cannula, and respiratory rate. Supplemental O₂ was given to participants as determined by the clinical opinion of the respiratory staff. Supplemental O₂ was noted if given to participants but not categorized as a serious adverse reaction requiring trial termination.

If at any time the participants experienced serious adverse reactions such as respiratory distress, stridor, or ETCO₂ greater than 60, PMV removal was scheduled (**Table 2**), and initiation of ventilatory support was planned. The trial would then be terminated and deemed unsuccessful. In the event of an unsuccessful PMV trial, the RCP would inform the IP and acquire ABG measurements. If this procedure did not improve the participant's respiratory condition, the next step would be to initiate ventilator support and request a chest X-ray.

Following night one, participants completed the Richards-Campbell Sleep Questionnaire (RCSQ) upon waking. The RCSQ is a six-question self-report questionnaire used to assess ICU patients' sleep quality.¹⁵ These six questions assess the domains of sleep depth, sleep latency, awakenings, ability to return to sleep, overall sleep quality, and overnight noise level.¹⁵ The responses were recorded on a 100 mm visual analog scale, with higher scores indicating better sleep levels than lower scores. The mean score represents the general perception of sleep quality, which was the secondary outcome of this study, evaluated by the sleep domain scores derived from the Richards-Campbell Sleep Questionnaire.

Tracheostomy Plug Trial – Day Two and Night Two

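### Read literally, any adverse event on the plug night withholds the sleep questionnaire and counts as failure; the valve night sets no questionnaire condition and fails only on serious reactions

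*Combined protocol and SAP*

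**What the plan says.** **Night one** (PMV Trial – Study Day One and Night One). The trial ends as unsuccessful if participants "experienced serious adverse reactions such as respiratory distress, stridor" or an ETCO₂ above 60, and Table 2 is cited. Supplemental oxygen is noted but "not categorized as a serious adverse reaction requiring trial termination". On the questionnaire the text reads: "Following night one, participants completed the Richards-Campbell Sleep Questionnaire (RCSQ) upon waking". No adverse-event condition is attached.

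**Night two** (Tracheostomy Plug Trial – Day Two and Night Two). The trigger is worded "Same as night one, if any adverse events or acute changes occurred", and the consequence is that "it was planned that the plug be removed, ventilator support would be started, and the trial considered a failure". The questionnaire has its own sentence: "If no adverse events occurred upon waking up following night two, the participants were again administered the RCSQ".

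**Statistical Analysis.** Paired t-tests or Wilcoxon signed-rank tests are planned for continuous variables. The analysis is complete case, with "only complete pairs of data from night one and night two at the three time points being included in the analysis".

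**The concern.** The study's two subjects are safety and sleep quality, and each patient is compared across the valve night and the plug night. That comparison is fair only if the same event has the same consequence on both nights. As worded, a non-serious event leaves night one intact but withholds the questionnaire on night two and may also count as a failure.

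The sleep outcome is the more exposed of the two. Whether it is recorded after the plug night depends on how well the plug was tolerated, and tolerance plausibly affects sleep. Missing questionnaires would then be related to the outcome itself, and a complete-case analysis does nothing to correct for that.

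**Working it through.** The documents state no event rate, sample size or power figure, so there is nothing to recompute. The check is a comparison of the two nights' rules, followed by the direction of any effect.

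**Step 1. The rules side by side**

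| Element | Night one (valve) | Night two (plug) |
|---|---|---|
| Severity needed for failure | Serious reactions | None stated; any event or acute change |
| ETCO₂ limit | Above 60 | Not repeated |
| Table 2 cited | Yes | No |
| Supplemental oxygen exempt | Yes | Not repeated |
| Adverse-event condition on RCSQ | None stated | No adverse events |

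The difference lies in the overnight rules. The daytime checks lack a severity word on both days, so they are not part of this point.

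**Step 2. What the opening words of the night-two sentence cover.** They introduce the trigger for plug removal and failure, so they can be read as importing the night-one threshold. The questionnaire condition is in a separate sentence with no reference back to night one. Had it been meant to match night one, it would carry no condition at all.

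**Step 3. Follow one non-serious event through each night.** On night one it does not end the trial, the questionnaire is completed, and the patient proceeds to night two, unless the event breaches a decannulation or study criterion. On night two, read literally, the questionnaire is not given. A paired test needs both nights, so the pair is lost. This holds whether or not the three-time-point wording in Statistical Analysis is taken to cover the RCSQ.

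**Step 4. Direction for sleep.** Let the paired difference be plug minus valve, with higher RCSQ scores better. Let q be the share of otherwise usable pairs lost through minor plug-night events, K the mean difference in kept pairs and L the mean difference in lost pairs.

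- Mean over all pairs = (1 − q)K + qL
- Complete-case mean = K
- Error = K − [(1 − q)K + qL] = q(K − L)

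If patients slept worse on plug nights with a minor event, L is below K. The error is then positive and flatters the plug. Neither q nor K − L can be obtained from the documents.

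**Step 5. Direction for failures.** If the literal trigger is applied, minor events count as failures on the plug night only. With two equally tolerated devices, that raises the plug's failure count. The two effects run in opposite directions, so the wording cannot be assumed to be conservative overall.

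**The case against.** The strongest reply is that night two is a shorthand cross-reference. It says it is the same as night one and lists the same consequences. Starting a ventilator for a trivial change in a patient who breathes unaided is implausible, so a serious threshold was probably meant. The phrase about acute changes also echoes the day-one wording, where the valve had to be "tolerated without any acute vital changes (i.e., adverse reactions" with Table 2 cited. That suggests one event list under several labels. Table 2 is not in the text reviewed; it may settle the matter, and its absence is not a fault of the plan. For the failure trigger this reply largely stands. A reader might infer that the plug was deliberately judged by a stricter failure standard, and the documents do not support that.

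The reply is weaker for the questionnaire. The cross-reference does not govern that sentence, and night one contains no matching condition to import. A single event list in Table 2 could still narrow what counts as an adverse event there.

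Three further points stand in part:

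- The Study Protocol section cancels participation whenever decannulation or study criteria are no longer met. These include being afebrile and hemodynamically stable. Some lesser night-one events would therefore also cost the pair, and the imbalance is limited to events that breach no criterion.
- Night two is reached only after a successful day and night one, so plug-night failures are already conditional on valve success. Aligning the wording would not make the two failure counts directly comparable. No between-night test of failures is explicitly specified either.
- Any numerical size would rest wholly on assumed rates, so none is offered.

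**Conclusion.** The point holds as a wording inconsistency that can bias the sleep comparison if it was followed. The questionnaire condition is the firmer part, because it is a stated rule that makes a paired outcome depend on tolerating one of the two devices. The failure trigger is the weaker part, because the night-one threshold may well have been intended.

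The direction for sleep rests on one assumption: that plug nights with a minor event were slept worse than those without. On that assumption the kept pairs may flatter the plug, while the failure count, read literally, may tilt against it. The size of either effect is unknown, and both could be zero if one threshold applied in practice to failure and to the questionnaire.

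A reader might go further and infer that pairs were in fact lost this way or that the result is biased. The documents do not show that. They report no events, no missing questionnaires and no results. The matter is worth considering and inexpensive to settle; confidence is medium.

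**What to change.** In Tracheostomy Plug Trial – Day Two and Night Two:

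1. Use the night-one trigger for failure: serious adverse reactions, including an ETCO₂ above 60, with Table 2 cited and supplemental oxygen stated not to be a failure.
2. Replace the questionnaire condition. Give the RCSQ on waking after both nights whether or not an adverse event occurred, provided the patient can complete it. Carrying the serious threshold over to the questionnaire would not be enough, since it would still omit the worst-tolerated nights.
3. Report the number of pairs lost on each night, with reasons.

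The document is written in the past tense and refers to study closeout, so conduct may no longer be open to change. In that case, state which failure rule and which questionnaire rule were applied on each night, and report the losses.

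The cost is a sentence or two of wording and a line in the results, with no extra patients or staff. The downside is that a few questionnaires would describe nights on which the device was removed. These should be flagged so that a reader can see how far the sleep result depends on them.

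### Only unpaired tests are named for categorical variables, so any yes/no variable compared between the two nights would be analysed as if the nights were different patients

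*Combined protocol and SAP*

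**What the plan says.** The title calls the trial "a Cross-Over Controlled Study". Each participant wears the speaking valve on night one. The section on day two and night two then says "If study day one and night one were successful, the protocol was continued to day two", and the same person wears the plug. No separate comparison group is described.

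In the Statistical Analysis section, "categorical data were described with frequencies", and the next sentence reads "Differences in categorical variables were evaluated using Fischer's exact test or Chi-Square testing as appropriate". The sentence after that reads "Differences in continuous variables were analyzed using paired t-tests for normally distributed data and Wilcoxon signed-rank test for non-normally distributed data". The section also restricts the analysis to patients with complete data from both nights. No paired test for categorical data is named, and no categorical variable or contrast is listed.

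**The concern.** Fisher's exact test and the ordinary chi-square test compare two sets of different people. Read naturally, the qualifier at the end of the quoted sentence only chooses between those two. The plan recognises pairing for continuous variables and leaves it out for categorical ones.

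If a yes/no item was compared between nights under this rule, its p-value takes no account of which patients changed. It may be too large or too small, and a reader cannot tell which, because neither the variables nor the groups are named. Supplemental oxygen is a possible example. The night-one text says its use was noted. The night-two text says "Again, nursing staff monitored and recorded heart rate, blood pressure, and temperature every four hours, and the RT on duty recorded oxygen saturation" and goes on to end-tidal carbon dioxide and respiratory rate, without mentioning supplemental oxygen.

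**Working it through.** **Inputs.** From the document: the two named tests, the same patients on both nights, and significance at p < 0.05. Sidedness is not stated, so two-sided is assumed. Sample size, event rates and within-patient correlation are not given. Everything numerical below is an illustration on assumed values, and there is no figure of the plan's own to reproduce.

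**Why pairing matters.** With n patients, night rates p1 and p2, and within-patient correlation φ, the variance of the difference in observed proportions is

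[p1(1−p1) + p2(1−p2) − 2φ√(p1(1−p1)p2(1−p2))] / n.

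The unpaired chi-square test leaves out the last term. With 30% on both nights, it works with 2 × 0.21 = 0.42 (over n), while the true value is 0.42 × (1 − φ). In large samples its real false-positive rate is therefore the two-sided normal tail beyond 1.96/√(1 − φ):

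- φ = 0.58: 1.96/√0.42 = 3.02, giving 0.25%.
- φ = −0.17: 1.96/√1.17 = 1.81, giving 7.0%.

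**Exact check of the false-positive rate.** All paired 2×2 tables were enumerated for n = 20 and 30% on both nights, with correlation set on a bivariate-normal latent scale (latent −0.3 is φ = −0.17; latent 0.8 is φ = 0.58).

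| Latent correlation | Chi-square | Fisher | Mid-p McNemar | Exact McNemar |
|---|---|---|---|---|
| −0.3 | 7.4% | 3.8% | 4.1% | 2.2% |
| 0 | 5.3% | 2.5% | 4.0% | 2.0% |
| 0.8 | 0.4% | 0.1% | 1.3% | 0.3% |

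**Power, 45% versus 15%** (each cell: zero correlation / latent 0.8).

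| Pairs | Chi-square | Fisher | Mid-p McNemar | Exact McNemar |
|---|---|---|---|---|
| 12 | 36.4 / 31.7% | 21.7 / 15.5% | 26.4 / 27.9% | 15.0 / 12.3% |
| 20 | 57.2 / 58.0% | 44.3 / 41.3% | 50.4 / 73.0% | 39.4 / 56.2% |
| 30 | 73.7 / 79.5% | 64.5 / 67.8% | 70.9 / 94.3% | 62.2 / 88.7% |

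**One set of totals, three pairings.** Take 8 of 20 positive on night one and 2 of 20 on night two. Chi-square = 40 × (8×18 − 2×12)² / (20×20×10×30) = 4.8, p = 0.028. Fisher gives p = 0.065. Neither changes with the pairing. McNemar uses only the patients who changed:

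- 2 positive on both nights, changes 6 and 0: exact p = 2 × 1/64 = 0.031; mid-p = 0.031 − 1/64 = 0.016.
- 1 positive on both, changes 7 and 1: exact p = 2 × 9/256 = 0.070; mid-p = 0.070 − 8/256 = 0.039.
- 0 positive on both, changes 8 and 2: exact p = 2 × 56/1024 = 0.109; mid-p = 0.109 − 45/1024 = 0.065.

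So the chi-square p-value can lie on either side of the paired one.

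**The case against.** The strongest reply is that no affected analysis is visible. The categorical sentence follows one on clinical and demographic characteristics and may refer only to those. The overnight measurements the text lists are continuous, and the sleep questionnaire uses a visual analogue scale. Supplemental oxygen is documented explicitly for night one only. Table 2 is not readable in the text available, so other yes/no items can be neither shown nor ruled out. Much of this stands, and it is why the point is conditional. It does not remove the gap: no separate patient groups are described, so who is compared with whom is unstated on the demographic reading too.

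Chi-square might also be taken loosely to cover McNemar's version. That is possible, but McNemar is not named, and listing chi-square beside Fisher's exact test points to the ordinary contingency-table choice.

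A third reply is that a paired test is not always better. This stands. With 12 pairs and latent correlation 0.3, mid-p has less power than chi-square (27.5% against 35.1%) and is more conservative (false-positive rate at 30% on both nights 1.85% against 3.04%). With 20 pairs at 0.3, power is level (57.1% against 57.6%).

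A reader might infer that a wrong test was actually used, or that false positives are likely. The document supports neither. No between-night categorical contrast is specified. Material inflation needs uncorrected chi-square with negative within-patient correlation, which nothing in the text suggests. Under positive correlation the cost is an over-conservative test, usually with lost power.

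**Conclusion.** The point holds in a limited form and is minor. The plan's only rule for categorical differences does not suit the only comparison the design describes, and it would give a p-value that ignores pairing for any yes/no variable compared between nights. Whether any such comparison was made cannot be determined from the document. The direction and size of the error depend on sample size, rates and correlation, none of which is given. On the assumed case of 20 patients at 30% on both nights, the actual chi-square false-positive rate runs from 0.4% to 7.4% over latent correlations 0.8 to −0.3. Continuous comparisons, including the sleep questionnaire, are unaffected.

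**What to change.** State which categorical variables were compared and between whom. If none was compared between nights, say so, and nothing needs re-running. Otherwise replace the sentence with:

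> Binary variables compared between night one and night two were analysed with a McNemar test (exact or mid-p) and reported as a paired difference in proportions with a 95% CI; Fisher's exact or chi-square tests were used only to compare different patients.

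Name one McNemar version for all variables before re-running. Mid-p is the more powerful: in the 12-pair illustration exact McNemar falls below even Fisher. A Newcombe paired score interval is one suitable CI. The plan is in the past tense and the title page reads "Use date of study closeout: 9/1/2016", so label any re-run post hoc.

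Do not test trial-ending events between nights. Only night-one successes reach night two, so complete pairs contain no night-one failures, and a paired test cannot repair that. Report these events per night, among patients who started that night, with exact 95% CIs. With no events the upper limit is 1 − 0.025^(1/n): 26.5% for 0 of 12, 16.8% for 0 of 20, 11.6% for 0 of 30.

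The cost is one or two sentences, no new data, and a binomial calculation on the discordant pairs. The downside is that with about 12 pairs, or near zero correlation, the paired test can have less power than uncorrected chi-square.

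### Does the plan need to name which ANOVA effect and which Tukey family answer the overnight vital-sign question?

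*Combined protocol and SAP*

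**What the plan says.** Two consecutive sentences in Statistical Analysis cover continuous data. The first reads: "Differences in continuous variables were analyzed using paired t-tests for normally distributed data and Wilcoxon signed-rank test for non-normally distributed data". The second applies two-way ANOVA with Tukey's "multiple comparisons post-hoc test were used to analyze differences in continuous variables at three time points (22:00, 02:00, and 06:00"). The sentence after that restricts the dataset to complete cases, "with only complete pairs of data from night one and night two at the three time points being included in the analysis". The significance rule is the same throughout: "Statistical significance was defined as a p-value less than 0.05".

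Under PMV Trial – Study Day One and Night One, nursing staff record heart rate, blood pressure and temperature every four hours, with the same three clock times given as examples. The respiratory therapist records oxygen saturation, ETCO₂ and respiratory rate, and no times are stated for these. The sleep questionnaire is completed once after each night. It is the only outcome given a rank: "The mean score represents the general perception of sleep quality, which was the secondary outcome of this study".

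The section does not name the ANOVA factors, the effect to be interpreted (night, night-by-time, or particular pairs) or the set of means over which Tukey is applied.

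**The concern.** Safety comes first in the title: "Assessing the Safety of Nighttime Passy-Muir Valve Use and its Impact on Sleep Quality". The two sentences on continuous data are the only stated tests of the overnight physiological readings. Read literally, a comparison of heart rate at 06:00 between the two nights fits both of them: a paired test under the first, an ANOVA with post-hoc pairs under the second. Within the ANOVA, the Tukey family could be:

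- the two nights at each time (one pair each);
- the three clock times (no pair compares valve with plug); or
- all six night-by-time means.

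These routes set different effective hurdles, so the same data could be reported as a difference or as no difference. In a safety comparison the strictest hurdle favours a finding of no difference. An unnamed effect also leaves room to pick a result after seeing the data.

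**Working it through.** **No figure to reproduce.** The document gives no sample size, SD, effect size or power. The values of n, the 0.5 SD difference, the correlations and two-sided testing below are assumptions. From the document come alpha = 0.05, two nights and three times.

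**Size of the Tukey family.** 2 × 3 = 6 cells, and 6 × 5 / 2 = 15 pairs. Of these, 3 compare the nights at the same time, 6 compare times within a night, and 6 differ in both.

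**Thresholds.** For one pair the critical value is t(0.975; df). For Tukey over k means it is q(0.95; k, df)/√2, which equals the t value when k = 2. At n = 20:

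| Error df | One pair | One of 15 pairs |
|---|---|---|
| 19 (own paired SD) | 2.09 | 3.16 |
| 38 | 2.02 | 3.00 |
| 95 | 1.99 | 2.91 |

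Dividing by √20 = 4.47, the smallest significant observed difference at df 19 is 2.09/4.47 = 0.47 SD against 3.16/4.47 = 0.71 SD.

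**Power for a true difference of 0.5 SD.** Noncentral t with noncentrality 0.5√n and df = n − 1:

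| n | One pair | One of 15 pairs |
|---|---|---|
| 10 | 29% | 7% |
| 20 | 56% | 22% |
| 30 | 75% | 40% |

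With df 38 or 95 at n = 20, power is 59 to 60% against 24 to 26%. The paired test and the single ANOVA pair are therefore close. The only large gap is between either of these and the 15-pair family.

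**Choice of effect.** This used 20,000 simulated trials per setting, n = 20, and a correlation of 0.5 between the between-night differences at different times. A 0.5 SD difference present at all three times makes the night main effect significant in 74% of trials and the night-by-time term in 5%. A difference at 02:00 and 06:00 only gives 41% and 59%. These terms answer different questions, so disagreement between them is expected and is not a fault in either.

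**What the text settles.**

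- *Which readings go to the ANOVA.* Its sentence is confined to three clock times. These are the times given for heart rate, blood pressure and temperature, so 06:00 heart rate is the clearest ANOVA case. The more specific sentence governs.
- *Which go to the paired tests.* The sleep score, taken once per night, has no time factor and can only go there.
- *Which factors.* A two-way ANOVA needs two. The complete-pairs sentence offers night and time, and no other crossed pair appears. The pairing also makes the comparison within-patient.
- *What stays open.* The effect interpreted, the Tukey family, and the allocation of oxygen saturation, ETCO₂ and respiratory rate. For these last three, the complete-pairs rule, written for the dataset as a whole at three time points, points to the ANOVA.

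**The case for a change.** The strongest case for a change is that the likeliest reading is still only inferred and that, even when it is granted, the effect and the Tukey family remain unstated. Those two choices produce the largest differences above. With no true difference, at least one of five candidate results (main effect, night-by-time term, three unadjusted same-time pairs) is significant in 15 to 17% of simulated trials at n = 20, against 5% for one named result. A few sentences would close the gap.

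The omission is real and the arithmetic reproduces, but less follows from it than appears. The 15 to 17% supposes an analyst who searches five results and reports any hit, and nothing in the document suggests this. The 56% against 22% contrast needs either Tukey applied to one pair at a time, where naming it would serve no purpose, or a paired test on readings that the ANOVA sentence already claims. Tukey over all cells is a conventional, conservative choice and not an error.

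A remedy would also have its own cost. Three unadjusted intervals per reading carry up to 1 − 0.95³ = 14% chance, if independent, that at least one excludes zero. A Bonferroni adjustment for three pairs lowers power from 56% to 37% at n = 20.

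**Conclusion.** No change to the plan follows. This is missing detail that a competent analyst fills from the text: night by time within patient for the repeated readings, and paired tests for once-per-night measures. The plan states no wrong rule here, and none of the possible readings would be invalid.

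The consequences are limited. The document's explicit safety rule is clinical and rests on serious adverse reactions, not on a p-value for vital signs. Those criteria and the sleep-score comparison are the same under every reading. The analysis is described in the past tense and the title page carries a closeout date, so what remains is clear labelling in the results: which effect is quoted and how many pairs Tukey covered. A non-significant Tukey pair should not be presented there as proof of no difference.

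The direction of the gap between 15 pairs and one pair does not depend on n: over n = 8 to 50 the 15-pair hurdle, with an ANOVA error term, is 1.26 to 1.45 times the paired-t hurdle. The power and error-rate figures are illustrations under assumed n, SD and correlation, and they do not describe this trial.
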